Note: The above does not apply to female subjects of nonchildbearing potential (ie, physiologically incapable of becoming pregnant) defined as:

 - has had a complete hysterectomy greater than or equal to 3 months prior to dosing or
 - has had a bilateral oophorectomy (ovariectomy) or
 - has had a bilateral tubal ligation or fallopian tube inserts or
 - is post-menopausal (a demonstration of a total cessation of menses for ≥1 year with a follicle stimulating hormone (FSH) level of >35 mIU/mL).
7. All male participants who have not had a vasectomy must use effective contraception from Day -1 to 90 days after their last dose of study drug. Effective contraception is defined as a condom and spermicide for the male, or condom and at least one of the following for a female partner:
 - Intrauterine device
 - Oral, injectable, implantable, transdermal, or intravaginal hormonal contraceptive
 - Be of non-childbearing potential
8. Male subjects must agree to refrain from sperm donation from the date of Screening until 90 days after their last dose of study drug
9. Subject must be willing and able to adhere to the assessments, visit schedules, prohibitions and restrictions, as described in this protocol

Exclusion Criteria

Subjects will not be eligible to participate in the study if they meet any of the following criteria:

1. Laboratory Screening Results:
 - Total bilirubin >ULN (normal range 0.2–1.2 mg/dL)

NOTE: Patients with Gilbert's syndrome will be allowed if they have a known history of

Gilbert's syndrome with a normal direct bilirubin value and normal reticulocyte count, and upon review by the medical monitor

- Total white blood cells (WBC) <3,000 cells/mm³
 - Absolute neutrophil count (ANC) <1,500 cells/mm³
 - Platelet count <140,000/mm³
 - Prothrombin time (international normalized ratio, INR)>1.2
 - Creatine kinase above the upper limit of normal (ULN) except when in relation with intense exercise
 - Serum creatinine >2 mg/dL or clearance creatinine <60 ml/min (based on Cockcroft-Gault method)
2. Known history of alpha-1-antitrypsin deficiency
 3. Use of an experimental treatment for NASH within the past 6 months
 4. Prior use and/or concurrent treatment with obeticholic acid (OCA)
 5. Use of immunosuppressant (eg, corticosteroids) for more than 2 weeks in duration within 1 year prior to Screening and during the course of the study
 6. Use of experimental or unapproved drugs within a year of Screening

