4.2 Secondary efficacy endpoint(s)

The secondary efficacy endpoints are as follows:

- Change from Baseline in percentage of fat in the liver as assessed by MRI-PDFF at Week 12
- Change from Baseline in liver stiffness as assessed by magnetic resonance elastography (MRE) at Week 12
- Change from Baseline of noninvasive liver fibrosis markers (ELF panel) and PRO C3 at Week 12
- Change from Baseline in NFS, APRI, and FIB-4 at Week 12
- Change from Baseline in TG, TC, HDL-C, LDL-C, adiponectin, and ApoA1, B, C3 at Week 12
- Change from Baseline in fasting glucose and insulin, HOMA index (in nondiabetic subjects) and HbA1c in subjects with T2DM at Week 12
- Change from Baseline in fibrinogen, CRP, IL6, IL1 β , TNF- α , TNF- β , alpha2 macroglobulin and haptoglobin levels at Week 12
- Pharmacokinetic parameters of EDP-305 (and metabolites): C_{max} , T_{max} , and AUC_{last}
- Change from Baseline in body weight at Week 12
- Change in waist to hip WTH ratio at Week 12
- Pharmacodynamic parameters of EDP-305: FGF19, C4, and bile acid (BA) at Week 12

In addition, the percentage change from Baseline in the primary endpoint and all secondary endpoints will be summarized (as applicable).

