5 SAMPLE SIZE AND POWER

Group sample sizes of 44 (in each dose group) and 22 placebo subjects achieves 80.438% power to reject the null hypothesis of equal means when the population mean difference in ALT is $(-40.0) - (-10.0) = -30.0$ with a standard deviation for both groups of 40.0 and with a significance level (alpha) of 0.050 using a two-sided two-sample equal-variance t-test. To account for a 10% discontinuation rate, 15 additional subjects will be enrolled to attempt to have at least 110 subjects who complete treatment bringing the total number of subjects enrolled to 125.

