7 STATISTICAL CONSIDERATIONS AND ANALYSIS

7.1 Derived variables

The below table provides the list of derived variables for demographic and baseline characteristics, various duration derivations, drug compliance, baseline derivations and other important derivations applicable for this study.

Table 3.

Variables	Formula
Demographic and Baseline characteristics	
Age at informed consent (in years)	floor ((date of informed consent – date of birth + 1)/ 365.25)
Body mass index (BMI) (kg/m ²)	weight (kg) / [height (m)] ²
Derivation of Duration	
Study day at any visit	Date of interest – date of first dose of study drug. One day is added if this difference is ≥ 0
Extent of Exposure (Days)	Date of last randomized study drug intake – Date of first randomized study medication intake + 1
Extent of Exposure (Weeks)	Extent of exposure (days)/7
Drug Compliance	
Compliance	$100 \times [1 - (\text{Number of days of study drug interruption}) / (\text{Extent of exposure (days)})]$
Baseline Derivations	
Baseline (Average)	The average of the screening and the day 1 values.
Baseline (Last value pre-dose)	Last non-missing values collected prior to the first dose of study drug
Screening	The value obtained at screening.
Change from Baseline	Post Baseline value – Baseline
Percentage change from Baseline	$[(\text{Change from Baseline}) / \text{Baseline}] * 100$
Other Derivations	
Creatinine Clearance (Cockcroft-Gault)	$CL_{Cr} (\text{mL/min}) = \{((140 - \text{age [years]}) \times \text{weight}) / (72 \times S_{Cr})\} \times 0.85$ (if female). S_{Cr} = serum creatinine
AST to Platelet Ratio Index (APRI)	$APRI = ([\text{AST (IU/L)} / \text{AST ULN (IU/L)}] / [\text{Platelets}(10^9/\text{L})]) \times 100$

	ULN = upper limit of normal
Fibrosis-4 score (FIB-4)	$FIB-4 = [Age \text{ (years)} \times AST \text{ (IU/L)}] / [Platelets \text{ (} 10^9/L) \times (\sqrt{ALT \text{ (IU/L)}})]$
NAFLD fibrosis score (NFS)	$NFS = -1.675 + 0.037 \times Age \text{ (years)} + 0.094 \times BMI \text{ (kg/m}^2) + 1.13 \times IFG/Diabetes \text{ (yes = 1, no = 0)} + 0.99 \times AST/ALT \text{ ratio} - 0.013 \times Platelets \text{ (} 10^9/L) - 0.66 \times Albumin \text{ (g/dL)}$

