A descriptive summary will be provided for PRO C3 values, change from Baseline and percentage change from Baseline using 8-number summary by visit and treatment group.

Change from Baseline and percentage change from Baseline PRO C3 at Week 12 will be analysed using an ANCOVA model with treatment as fixed effect and the associated Baseline value as covariate. Least squares means and standard errors will be presented for each visit, p-value and 2-sided 95% confidence interval for treatment differences will be presented for each visit. Significance tests will be based on least-squares means using a two-sided $\alpha = 0.05$.

A by-subject listing will be provided for observed and derived variables.

8.6.3.4 Change from baseline and percentage change from baseline in fibrosis at week 12

Fibrosis will be estimated using the APRI, the fibrosis 4 (FIB-4) formulae, and the NAFLD fibrosis score (NFS).

NFS at Week 12

The NFS will be calculated by the central laboratory using the following formula:

$$-1.675 + 0.037 \times \text{Age (years)} + 0.094 \times \text{BMI (kg/m}^2\text{)} + 1.13 \times \text{IFG/Diabetes (yes = 1, no = 0)} + 0.99 \times \text{AST/ALT ratio} - 0.013 \times \text{Platelets (10}^9\text{/L)} - 0.66 \times \text{Albumin (g/dL)}$$

NFS online calculator reference:

<https://www.mdcalc.com/naflid-non-alcoholic-fatty-liver-disease-fibrosis-score>

A descriptive summary will be provided for NFS values, change from Baseline and the percentage change from Baseline using 8-number summary by visit and treatment group.

Change from Baseline and percentage change from Baseline in NFS at Week 12 will be analysed using an ANCOVA model with treatment as fixed effect and the associated Baseline value as covariate. Least squares means and standard errors will be presented for each visit, p-value and 2-sided 95% confidence interval for treatment differences will be presented for each visit. Significance tests will be based on least-squares means using a two-sided $\alpha = 0.05$.

A by-subject listing will be provided for observed and derived variables.

APRI at Week 12

The APRI will be calculated by the central laboratory using the following formula:

$$([\text{AST IU/L} / \text{AST ULN}] / [\text{Platelet count } 10^9\text{/L}]) \times 100 = \text{APRI}$$

Online calculator can be found at: <http://www.hepatitisc.uw.edu/page/clinical-calculators/apri>

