8.6.4.3 Exploring Relationships between Endpoints

Relationships between the endpoints will be evaluated as follows:

- Comparing the percentage change in ALT to the proportion of subjects with at least a 30% reduction in the percentage change from baseline in the MRI-PDFF score
- Comparing the percentage change in the WTH ratio to the proportion of subjects with at least a 30% reduction in the percentage change from baseline the MRI-PDFF at Week 12
- Comparing the percentage change in PRO-C3 to the proportion of subjects with at least a 30% reduction in the percentage change from baseline the MRI-PDFF at Week 12
- Comparing the percentage change in ALT to the proportion of subjects with at least a 15% reduction in the percentage change from baseline in the MRE at Week 12
- Comparing the percentage change in the WTH ratio to the proportion of subjects with at least a 15% reduction in the percentage change from baseline the MRE at Week 12
- Comparing the percentage change in PRO-C3 to the proportion of subjects with at least a 30 point reduction in ALT at Week 12
- Comparing the percentage change in body weight to the proportion of subjects with at least a 30 point reduction in ALT at Week 12
- Comparing the percentage change in PRO-C3 to the proportion of subjects with at least a 20 percent reduction in ALT at Week 12
- Comparing the percentage change in body weight to the proportion of subjects with at least a 20 percent reduction in ALT at Week 12
- Comparing the percentage change in body weight to the proportion of subjects with at least a 30% reduction in the percentage change from baseline in MRI-PDFF at Week 12
- Comparing the percentage change in body weight to the proportion of subjects with at least a 15% reduction in the percentage change from baseline in MRE at Week 12

In addition, relationships between the primary and secondary endpoints will be explored using scatterplots (and correlation coefficients) using various change and percent change from baseline. All data points will be included for all visits on a single plot, with separate color for each treatment group.

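### SAP 8.6.3.4 tests percentage change in NFS, a score that can be negative or zero, so the result has no consistent direction; one QTcF summary category in SAP 8.7.6 also describes only pre-dose values

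*SAP*

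**What the plan says.** **NFS.** The named secondary endpoint, in SAP 4.2 and likewise in protocol 2.2.2 and 11.6.1, is "Change from Baseline in NFS, APRI, and FIB-4 at Week 12". SAP 4.2 then adds a general sentence: "In addition, the percentage change from Baseline in the primary endpoint and all secondary endpoints will be summarized (as applicable". SAP 8.6.3.4 goes further for NFS. It orders a summary ("A descriptive summary will be provided for NFS values, change from Baseline and the percentage change from Baseline using 8-number summary") and a test ("Change from Baseline and percentage change from Baseline in NFS at Week 12 will be analysed using an ANCOVA model"), with a confidence interval and a two-sided 0.05 significance test. Table 3 in SAP 7.1 defines "Percentage change from Baseline" as change divided by Baseline, times 100. It takes no absolute value of the denominator and has no rule for a Baseline at or below zero. SAP 8.6.4.3 adds that "relationships between the primary and secondary endpoints will be explored using scatterplots (and correlation coefficients) using various change and percent change from baseline", which could take in the same derived value.

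**QTcF.** SAP 8.7.6 counts three things as significant ECG changes: a rise in QTcF of more than 60 msec, a QTcF above 500 msec, and a QTcF above 450 msec (males) or 470 msec (females) at screening or Baseline.

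**Causality.** SAP 8.7.1 treats an adverse event as related if causality is probable or possible, and counts missing causality as related. Protocol 9.2.2 has four labels: Related, Possibly Related, Unlikely Related and Not Related. Protocol 9.2.5 records SAEs on the SAE form at two levels, related or not related.

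**The concern.** A percentage change is interpretable when the baseline is positive and well away from zero. APRI and FIB-4 are positive ratios, so they raise no problem of sign. NFS has a negative constant and subtracts platelet and albumin terms, so it is not bounded at zero. Dividing by a signed baseline gives two subjects with the same clinical change opposite signs, and gives a subject near zero a very large value. The absolute-change and percentage-change tests of NFS can then disagree for arithmetic reasons alone, and the percentage-change p-value would stand in the report without a direction that a reader could use.

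The QTcF clause is a smaller matter of the same kind, a derivation rule that does not measure what its label says. A value taken before dosing cannot be a change on treatment.

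**Working it through.** **1. Inputs.** The NFS formula is in SAP 7.1 and 8.6.3.4, and the percentage-change formula in Table 3. The lower platelet limit comes from the exclusion "Platelet count <140,000" per mm³. The documents give no baseline distribution for NFS, so the subject below is an assumed one: age 50, BMI 34, diabetic, AST 50, ALT 80, albumin 4.4.

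**2. Baseline at platelets 240.**
-1.675 + 0.037×50 + 0.094×34 + 1.13 + 0.99×(50/80) - 0.013×240 - 0.66×4.4 = -0.904.
Each 1-unit fall in platelets adds 0.013, so the score is -0.124 at 180 and +0.136 at 160. It is zero at 240 - 0.904/0.013 = 170.4, inside the eligible range.

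**3. One change, three baselines.**
- Rise: ALT 80 to 60 with AST held gives 0.99×(50/60 - 50/80) = +0.206.
- Fall: BMI 34 to 32 only gives -0.094×2 = -0.188.

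| Platelets | Baseline NFS | Rise of 0.206 | Fall of 0.188 |
|---|---|---|---|
| 240 | -0.904 | -22.8% | +20.8% |
| 180 | -0.124 | -166.0% | +151.3% |
| 160 | +0.136 | +151.9% | -138.5% |

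Group means inherit the problem. Two subjects who both rise by 0.206 average (-22.8 + 151.9)/2 = +64.6% if their platelets are 240 and 160, but (-22.8 - 166.0)/2 = -94.4% if they are 240 and 180. This is algebra and needs only that baselines can lie on both sides of zero.

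**4. Illustration at trial size.** The plan states no power for NFS. Its ALT calculation uses "Group sample sizes of 44 (in each dose group) and 22 placebo subjects", a difference of 30 and an SD of 40. A noncentral-t calculation gives 80.76% against the stated 80.438%, which is close enough. The simulation borrows that standardized effect, 30/40 = 0.75, as an assumed NFS effect of -0.3 with change SD 0.4. It uses 44 against 22 subjects, normal baselines, ANCOVA with the baseline covariate, two-sided 0.05 and 4,000 trials per setting.

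| Assumed baseline mean, SD | Absolute change: power | Percentage change: rejects | Percentage change: estimate has wrong sign |
|---|---|---|---|
| -2, 1.0 | 80.4% | 26.0% | 82% |
| -1.5, 1.4 | 80.8% | 5.0% | 64% |
| -1, 1.0 | 80.2% | 4.8% | 62% |
| 0, 1.0 | 80.3% | 2.4% | 50% |
| +0.5, 1.0 | 79.3% | 2.6% | 45% |

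In the first row essentially all the rejections are in the wrong direction. With a true effect of -0.1 in that setting, wrong-direction significance is about 6% and the power of absolute change about 16%. At baseline means of 0 or +0.5, with the effect of -0.3, wrong-direction significance is about 1% or less and the test is mostly noise.

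**5. QTcF, text against text.** Exclusion criterion 19 in protocol 3.2 uses the same 450/470 msec thresholds at the same two time points. Anyone who meets the SAP category should not have been enrolled, so the row can hold only eligibility deviations. The other two criteria work on treatment. Between them, a post-baseline value above 450/470 and up to the smaller of 500 and Baseline + 60 has no QTcF-specific category. For a male at 420 msec that is above 450 to 480; for a female at 440 msec, above 470 to 500. There is no such band at baselines of 390 or less (males: 390 + 60 = 450) or 410 or less (females: 410 + 60 = 470).

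**6. Causality.** Probable is not a label in protocol 9.2.2, and the SAP rule does not name Related. Two of the seven summaries listed in SAP 8.7.1 use the rule: treatment-related TEAEs and treatment-related SAEs.

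**The case against.** The best case for leaving the text alone is that nothing depends on it. The named NFS endpoint is absolute change, its valid ANCOVA is ordered in the same sentence, and percentage change is an added output for one of many secondary variables. That stands, and it sets the severity. It does not make the percentage-change test meaningful. The qualifier at the end of the general sentence in SAP 4.2 does not help either, because SAP 8.6.3.4 orders the test for NFS explicitly.

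Three stronger readings are tempting and are not supported.

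- *The trial would probably report an NFS benefit as significant harm.* The 26% comes from the most extreme of the assumed settings, and the effect size is borrowed from ALT. A fall of 0.3 through BMI alone would need 0.3/0.094 = 3.2 kg/m² in 12 weeks. The documents support an uninterpretable direction, not a rate of false harm.
- *On-treatment QTcF between 450/470 and 500 msec goes uncounted.* SAP 8.7.6 also counts the overall ECG interpretation by treatment group and time point, and the values appear in the by-visit summaries and listings. Only a QTcF-specific category is missing, and protocol 11.7.3 does not promise one at 450/470 msec.
- *Events that the investigator labels Related will be dropped.* SAP 1 says the plan is to be read with the CRF, whose labels are not available here. An analyst would almost certainly count Related as related, and the number of events affected may be zero.

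The link to SAP 8.6.4.3 is also only potential, since none of the comparisons listed there names NFS.

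**Conclusion.** The NFS percentage-change analysis is wrong as written. The proof is the formula itself: it assumes only that eligible baselines can fall on both sides of zero, which the worked subject shows within the eligible platelet range. The simulation is illustrative and rests on an assumed baseline distribution, effect and change SD.

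The QTcF clause is also wrong as written, but small: it describes a pre-dose eligibility threshold under the label of a change. The causality wording is a mismatch to be clarified, not a demonstrated error.

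None of this touches the primary ALT analysis, the overall frequencies of AEs, SAEs and AEs leading to discontinuation, or the named NFS endpoint. Severity is minor. Confidence is high for NFS and QTcF; the causality item cannot be settled without the CRF.

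**What to change.** - **SAP 8.6.3.4:** delete the percentage-change summary and ANCOVA for NFS and analyse absolute change only. State in SAP 8.6.4.3 that NFS percentage change is not used in any scatterplot or correlation.
- **SAP 8.7.6:** remove the screening/Baseline clause from the list of significant changes, or apply that summary category to post-baseline ECGs. This concerns the summary table only.
- **SAP 8.7.1:** check the causality labels on the CRF, align the SAP wording with them and with protocol 9.2.2, and state how the two-level SAE form in protocol 9.2.5 maps to the same definition.

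The cost is three short edits, which the SAP's own provision for an amended version before database lock already allows. No new data or subjects are needed, and no planned endpoint is lost.

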8.6.4 Additional Analyses (Liver Tests)

8.6.4.1 Change from Baseline and Percentage Change from Baseline in Additional

Liver Parameters

AST by Visit and at Week 12

A descriptive summary will be provided for AST values, change from Baseline and percentage change from Baseline using 8-number summary by visit and treatment group.

Change from Baseline and percentage change from Baseline in AST at each visit, with the Week 12 being the primary visit of interest, will be analysed using an ANCOVA model with treatment as fixed effect and the associated Baseline value as covariate. Least squares mean and standard errors will be presented for each visit, p-value and 2-sided 95% confidence interval for treatment differences will be presented for each visit. Significance tests will be based on least-squares means using a two-sided $\alpha = 0.05$.

By-subject listing will be provided for observed and derived variables.

Total Bilirubin by Visit and at Week 12

A descriptive summary will be provided for Total Bilirubin values, change from Baseline and percentage change from Baseline using 8-number summary by visit and treatment group.

Change from Baseline and percentage change from Baseline in Total Bilirubin at each visit, with the Week 12 being the primary visit of interest, will be analysed using an ANCOVA model with treatment as fixed effect and the associated Baseline value as covariate. Least squares means and standard errors will be presented for each visit, p-value and 2-sided 95% confidence interval for treatment differences will be presented for each visit. Significance tests will be based on least-squares means using a two-sided $\alpha = 0.05$.

By-subject listing will be provided for observed and derived variables.

GGT by Visit and at Week 12

A descriptive summary will be provided for GGT values, change from Baseline and percentage change from Baseline using 8-number summary by visit and treatment group.

Change from Baseline and percentage change from Baseline in GGT at each visit, with the Week 12 being the primary visit of interest, will be analysed using an ANCOVA model with treatment as fixed effect and the associated Baseline value as covariate. Least squares means and standard errors will be presented for each visit, p-value and 2-sided 95% confidence interval for treatment differences will be presented for each visit. Significance tests will be based on least-squares means using a two-sided $\alpha = 0.05$.

By-subject listing will be provided for observed and derived variables.

Alkaline Phosphatase by Visit and at Week 12

A descriptive summary will be provided for alkaline phosphatase values, change from Baseline and percentage change from Baseline using 8-number summary by visit and treatment group.

Change from Baseline and percentage change from Baseline in alkaline phosphatase at

each visit, with the Week 12 being the primary visit of interest, will be analysed using an ANCOVA model with treatment as fixed effect and the associated Baseline value as covariate. Least squares means and standard errors will be presented for each visit, p-value and 2-sided 95% confidence interval for treatment differences will be presented for each visit. Significance tests will be based on least-squares means using a two-sided $\alpha = 0.05$.

By-subject listing will be provided for observed and derived variables.

8.6.4.2 Subgroup Analyses

Subgroup analyses will be performed on selected outcomes in subgroups of interest. All subgroup analyses will be exploratory in nature. As the interest will be on how different treatment regimens work in a specific subgroup, instead of whether the treatment differences are the same across different subgroups, the subgroup analyses will be performed by analyzing the outcome data in different subgroups, instead of analyzing the outcome data in the whole population with subgroup factors included in the analyses model.

Subgroup analyses will be performed for the primary endpoint and the secondary endpoints to determine whether significant differences exist in primary and secondary endpoint results between subgroups.

These subgroup analyses will be carried out using the subjects from the efficacy population.

The list of potential subgroups (with applicable definitions in parentheses) includes the following:

- MRE Week 12 response: (<15% reduction vs \geq 15% reduction in percentage of change from baseline)
- MRI-PDF Week 12 response: (<30% reduction vs \geq 30% reduction in percentage of change from baseline)
- Both MRE Week 12 response (\geq 15% reduction in percentage of change from baseline) and MRI-PDF Week 12 response (\geq 30% reduction in percentage of change from baseline) vs non-response
- NASH Diagnosis (biopsy vs phenotype)
- ALT Week 12 Category (\geq 0 change from baseline
 - (0--10] change from baseline
 - (-10--20] change from baseline
 - (-20--30] change from baseline
 - (-30--40] change from baseline
 - <-40 change from baseline) AND same ALT categories for percent change from baseline

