8.6.3 Analysis of secondary efficacy endpoint(s)

All analysis of secondary efficacy endpoints will be performed on the efficacy population. Additional analyses will be performed on the per protocol population. All secondary endpoint related to PK data will be analysed using subjects in the PK population. Endpoints related to PD data will be analyzed using subjects in the efficacy population unless otherwise specified.

8.6.3.1 Change from baseline and percentage change from baseline in percentage of fat in the liver as assessed by MRI-PDFD at week 12

Percentage of fat in the liver assessed by MRI-PDFD at Screening and Week 12, change from Baseline and percentage change from Baseline will be summarized using an 8-number summary by visit and treatment group.

The screening visit will be considered the Baseline value for this endpoint.

Change from Baseline and percentage change from Baseline in percentage of fat in the liver at Week 12 will be analysed using an ANCOVA model with treatment as fixed effect and the associated Baseline value as covariate. Least squares mean and standard errors will be presented for each visit, p-value and 2-sided 95% confidence interval for treatment differences will be presented for each visit. Significance tests will be based on least-squares means using a two-sided $\alpha = 0.05$.

In addition, the proportion of subjects who show at least a 30% reduction versus those less than a 30% reduction from Baseline in liver fat assessed by MRI-PDFD at Week 12 will be summarized (*Loomba et.al, 2018*)^[OBJ]. Inferential testing will be performed using a Fisher's Exact test to compare each of the active arms to the placebo arm. All subjects in the efficacy population will be included in this analysis, with those subjects with missing Week 12 MRI-PDFD results included in the denominator (i.e., Missing=failure). The ALT value change from Baseline in ALT and percentage change from Baseline in ALT at week

12 will be summarized by treatment and liver fat response rate. The ANCOVA model will be repeated as described above, adding in the subgroup as a fixed effect.

A by-subject listing will be provided for observed and derived variables.

8.6.3.2 Change from baseline and percentage change from baseline in liver stiffness as assessed by MRE at week 12

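### Exploratory subgroup comparisons in SAP 8.6.4.2 mostly condition on Week 12 outcomes: the treatment effect largely disappears when an endpoint is analysed within its own categories, and can be biased within imaging-response groups

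*SAP*

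**What the plan says.** SAP 8.6.4.2 (Subgroup Analyses) covers the primary and secondary endpoints. Its first paragraph gives the purpose: "As the interest will be on how different treatment regimens work in a specific subgroup". The outcome data are therefore analysed separately within each subgroup, and the section expressly declines to put subgroup factors into a whole-population model. Its second paragraph gives a different purpose: "Subgroup analyses will be performed for the primary endpoint and the secondary endpoints to determine whether significant differences exist" between subgroups.

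The list of potential subgroups has five factors:

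- "MRE Week 12 response", cut at a 15% reduction
- "MRI-PDF Week 12 response", cut at a 30% reduction
- both responses combined, versus non-response
- NASH diagnosis, by biopsy or by phenotype
- "ALT Week 12 Category": no fall, four 10-unit bands down to -40, and below -40, with the same bands for percent change

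Nothing exempts ALT from the ALT categories, or MRI-PDFF and MRE from their own response groups. The section also states: "All subgroup analyses will be exploratory in nature".

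SAP 8.6.3.1 defines liver-fat response at Week 12, summarises ALT by treatment and response, and then repeats the ANCOVA, "adding in the subgroup as a fixed effect".

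SAP 8.1 sets two-sided testing at 0.05 unless otherwise stated, and SAP 8.6.1.1 makes no multiplicity adjustment.

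**The concern.** A subgroup comparison between arms keeps the protection of randomisation only if the subgroup is fixed before treatment can affect it. Here four of five factors are measured after 12 weeks of treatment, and each is something the drug is meant to change.

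The clearest case is ALT. The primary endpoint is change in ALT at Week 12, and one subgroup factor is change in ALT at Week 12. Comparing arms within a narrow band of ALT change means comparing subjects selected because their changes are nearly equal. The drug effect then appears in how many subjects reach each band, and hardly at all inside the bands. The same logic applies to MRI-PDFF and MRE within their own response groups.

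For ALT within imaging-response groups the problem is different. If the drug affects who responds, placebo responders and active responders are different kinds of subject, and the difference between them mixes drug effect with selection.

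At stake is how the exploratory tables are read. Without a caveat, they could suggest a weaker drug effect than exists, or a responder population that selection has produced.

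**Working it through.** **Inputs.** From SAP 5: mean ALT change -40 (active) and -10 (placebo), SD 40 in both, 44 subjects per dose and 22 on placebo, two-sided 0.05, stated power 80.438%. From SAP 8.6.4.2: the ALT categories. The documents give no imaging response rates and no correlation between ALT and imaging change, so those are assumed below.

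**1. The plan's own figure.** Noncentrality = 30 / (40 × √(1/44 + 1/22)) = 2.872 with 64 degrees of freedom. The noncentral t gives power of 80.76%, within about 0.3 points of the stated value, so the planning inputs are read correctly.

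**2. ALT change within ALT-change categories.** For a normal variable with mean μ and SD σ, the mean between limits a and b is μ + σ[φ(α) − φ(β)] / [Φ(β) − Φ(α)], with α = (a − μ)/σ and β = (b − μ)/σ. The denominator is the share of subjects in the category.

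| ALT change | Share active / placebo | Expected n (of 44 / 22) | Mean active / placebo | Difference |
|---|---|---|---|---|
| ≥ 0 | 15.9% / 40.1% | 7.0 / 8.8 | 21.01 / 28.54 | -7.5 |
| 0 to -10 | 6.8% / 9.9% | 3.0 / 2.2 | -5.18 / -5.03 | -0.16 |
| -10 to -20 | 8.2% / 9.9% | 3.6 / 2.2 | -15.13 / -14.97 | -0.16 |
| -20 to -30 | 9.3% / 9.3% | 4.1 / 2.0 | -25.08 / -24.92 | -0.16 |
| -30 to -40 | 9.9% / 8.2% | 4.3 / 1.8 | -35.03 / -34.87 | -0.16 |
| < -40 | 50.0% / 22.7% | 22.0 / 5.0 | -71.92 / -63.15 | -8.8 |

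Weighting each difference by n₁n₂/(n₁ + n₂) gives weights of 3.90 (≥ 0), 5.25 (the four bands together) and 4.06 (< -40). The average is (3.90 × -7.54 + 5.25 × -0.16 + 4.06 × -8.76) / 13.21 ≈ -5.0. About 83% of the -30 is removed (1 − 5/30). The benefit is visible in the share columns.

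In 20,000 simulated trials (44 versus 22), the 10-unit bands held at least two subjects per arm in only 51–58% of trials. Where a t-test was possible, it rejected in 5.4–5.7% of trials in those bands, 9.0% in ≥ 0 and 6.2% in < -40, against 80.8% for the overall comparison. The percent-change bands were not calculated, because the SAP gives no planning values on that scale.

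**3. ALT change within imaging-response groups (illustration).** Take bivariate normal ALT and imaging change, with assumed response of 20% on placebo and 45% on active. As the within-arm correlation goes from 0 to 0.7, the ALT difference moves from -30 to about -15 in responders and from -30 to about -20 in non-responders. If the response rates are equal (20% in both arms), it stays at -30 at every correlation. If the drug changes imaging response but not ALT, correlations of 0.3 to 0.7 produce spurious differences against the drug of +6 to +15 (responders) and +4 to +10 (non-responders).

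**4. Responder status as a fixed effect, taking ALT as the outcome (illustration).** The adjusted treatment coefficient is -30 − c(p₁ − p₀). Here p₁ and p₀ are the active and placebo response rates, and c is the pooled within-arm difference in ALT change, responders minus non-responders. Within an arm, that difference is -40ρφ(z)/[p(1 − p)], where z is the normal quantile of p. Arms are weighted by n·p(1 − p).

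- For p₀ = 0.10, p₁ = 0.50 and ρ = 0.6, the within-arm differences are -46.8 (placebo) and -38.3 (active).
- With 2:1 weights, c ≈ -39.6, and the coefficient is -30 + 39.6 × 0.40 ≈ -14.2.
- Over 10–20% placebo response, 40–50% active response and ρ from 0 to 0.6, the coefficient runs from -30 (no bias at ρ = 0) to about -14.

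**5. The text of 8.6.3.1.** The ANCOVA described earlier in that section has liver fat as its outcome, while the sentence just before the repeated model concerns ALT. If ALT is meant, treatment is adjusted for another effect of the drug. If liver fat is meant, it is adjusted for its own dichotomised value. Both condition on a post-randomisation outcome.

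**The case against.** The strongest reply is that the SAP calls these analyses exploratory, speaks of selected outcomes and potential subgroups, and leaves the primary ANCOVA in the whole efficacy population. The overall estimate would be reported alongside. All of this stands, and it limits the harm. It does not make the within-category estimates interpretable.

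A second reply is that the second paragraph of 8.6.4.2, read alone, describes comparing responders with non-responders, an association like those in 8.6.4.3. The section also specifies no model or treatment contrast of its own. That too is fair. But the first paragraph speaks of how treatment regimens work inside a subgroup, so the between-arm reading is the likelier one. The two aims need reconciling in any case.

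Third, a reader might infer that the drug effect is removed by construction in all of these subgroups. The documents do not support that. Near-complete removal applies to ALT in the four 10-unit bands, which hold about a third of subjects. The two end categories keep about 25–29% of the planned difference. Within imaging-response groups the effect is biased by an unknown amount, possibly zero. NASH diagnosis is a sound baseline subgroup.

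Finally, valid response comparisons are already planned: 8.6.3.1 and 8.6.3.2 test response proportions between arms with Fisher's exact test and describe ALT by treatment and response. These can stay.

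**Conclusion.** The point holds for exploratory analyses only. Under the SAP's planning values and normality, analysing ALT change within its own Week 12 categories reduces the -30 IU/L difference to about -0.16 in each 10-unit band, -7.5 in ≥ 0 and -8.8 in < -40. By the same reasoning, MRI-PDFF and MRE should not be compared between arms within their own response groups.

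For ALT and other endpoints within imaging-response groups, randomised comparability is lost. The range of -30 to about -14 for a responder-adjusted ALT coefficient is an illustration. It depends on assumed response rates and correlations, and on reading ALT as the outcome in 8.6.3.1, which the text leaves open. It should not be quoted as the bias in this trial.

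It would also be wrong to infer that the trial's efficacy conclusion is at risk. The primary ANCOVA in SAP 8.6.2 does not condition on any Week 12 outcome. What would mislead is the set of treatment estimates and p-values inside outcome-defined groups.

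**What to change.** In SAP 8.6.4.2:

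- Limit between-arm subgroup comparisons to the baseline factor already listed, biopsy versus phenotype.
- Remove the ALT Week 12 category as a subgroup for ALT, and likewise MRI-PDFF and MRE within their own response groups.
- Present Week 12 response groups only descriptively by arm, or as associations between endpoints as in 8.6.4.3, without treatment p-values.
- State one aim in place of the two that now conflict.

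In SAP 8.6.3.1, drop the ANCOVA with responder status as a fixed effect. Alternatively, name its outcome and label it an association between endpoints that gives no treatment estimate.

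The cost is SAP wording and somewhat fewer tables; no data collection changes. The sponsor loses p-values within responder groups, which could not have been interpreted as drug effects.
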